4.3.4. Periprocedural and Discharge Clinical Utility Measures

The following periprocedural through discharge clinical utility measures will be summarized using descriptive statistics.

- 1. Mean duration (min) of procedure.
- 2. Mean time (min) to implant the LSA Branch device.
- 3. Proportion of subjects who underwent general anesthesia.
- 4. Mean volume (cc) of estimated blood loss.
- 5. Proportion of subjects requiring blood transfusions.
- 6. Mean time (hours) in intensive care unit.
- Mean time (days) of overall hospital stay (from hospital admission to discharge).

5. Investigation Plan

This study is a prospective, single-arm, non-randomized, multicenter, pre-market clinical study evaluating subjects implanted with the Valiant Mona LSA Thoracic Stent Graft System for the treatment of aneurysms, type B chronic dissections, and penetrating ulcers of the descending thoracic aorta who are candidates for revascularization of the left subclavian artery. All analyses will be descriptive in nature and no statistical comparisons are planned. This study is not a hypothesis driven study; no hypotheses testing will be carried out.

6. Determination of Sample Size

There is no sample size calculation since this study is not a hypothesis driven study; however, the number of enrolled subjects is pre-specified. This study will enroll up to 44 subjects.

Statistical Methods 7.

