7.9.3. Additional Observations

7.9.3.1. Major Adverse Events and Major Clinical Events

The following observations will be assessed through clinical follow-up (office visit or phone contact):

- Major adverse events (MAEs) rates within 30 days of the initial or secondary procedures, including:
 - All-Cause Mortality
 - Myocardial Infarction
 - Paraplegia
 - Renal Failure
 - Stroke
 - Left Arm/Hand Ischemia
- Secondary endovascular procedures
- Rupture
- Conversion to surgery
- Surgical revascularization of the LSA
- **Paraparesis**

[figure not shown]
The rate of the above events will be calculated on the subject level, and for different reporting time points, the correspondent cutoff days will be used as shown in Table 3.

For each visit (or reporting time point), the event rate will be calculated as the proportion of the number of subjects with a certain event term over the number of evaluable subjects. The evaluable subjects at each reporting time point include all subjects who are enrolled by the snapshot date and

- 1) Had a clinical or safety event (e.g. MAE) within (on or before) the Reporting cutoff Days, or
- 2) Had a follow-up or days to last contact at or after the lower limit of the Reporting Window,

Revision [6.0]

Page 19 of 27

[figure not shown]
3) The Withdrawal Consent Date /Recorded Lost-to-Follow-up Date at or after the lower limit of the Reporting Window

'Days to MAE' (date of earliest MAE – date of index procedure) and 'Days to Last Contact' (date of last contact – date of index procedure) are usually used for the determination of the eligibility of the 'evaluable subject'. The last contact date will be calculated based on the information gathered from all available dates during the follow-ups.

Similarly, 'Days to any AEs' and 'evaluability' of any AEs will be determined with the same principle as described above.

- 1. For death, Use the date of death from the CEC form, if it is not available then use Date of Death from study exit form.
- 2. For withdrew ("Subject withdrew consent to participate in the study" or " Physician's decision to protect the welfare of the subject") or "Subject enrolled but not implanted, completed 1 month follow-up", use Date of Exit from study exit form.
- 3. For patients who exited study for LTF, complete FU, or other reason, use last known date in the study from:
 - 1) Adverse Event Form
 - (i) Date event started
 - (ii) Date of resolution
 - 2) Secondary Procedure Form: Date of secondary procedure

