 - 3) Conversion to Open Repair Form: Date of Open Repair procedure
 - 4) Clinical follow-up Form (including unscheduled)
 - (i) Date physical exam performed
 - (ii) Date of Labs:
 - 5) Imaging follow-up Form: Date of diagnostic imaging (including unscheduled imaging)
 - 6) For patients who exited study with no follow-up, use last known date in the study from:
 - (i) Procedure Form: Date of procedure
 - (ii) Discharge Form: Date of discharge

Revision [6.0] Page 20 of 27

7) For Patients who did not exit study - Use last known date as above.

The 'Reporting Cutoff Days', 'Lower limit of the Reporting Window' and the correspondent visits are listed in Table 3:

Table 3. Reporting Window for MAE and Major Clinical Events

Visit	Reporting Cutoff Days	Lower Limit of the Reporting Window		
1-month	30 days post-index procedure	Days to last contact: 15 days post-index procedure		
6-month	183 days post-index procedure	Days to last contact: 153 days post-index procedure		
12-month	365 days post-index procedure	Days to last contact: 335 days post-index procedure		
24-month	730 days post-index procedure	Days to last contact: 674 days post-index procedure		
36-month	1095 days post-index procedure	Days to last contact: 1039 days post-index procedure		
48-month	1460 days post-index procedure	Days to last contact: 1404 days post-index procedure		
60-month	1825 days post-index procedure	Days to last contact: 1769 days post-index procedure		

In addition to the point estimate of the rate for each event at each time point, a two-sided 95% Confidence Interval will also be calculated for each correspondent point estimate using the exact binomial method.

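### SAP 7.9.3.1, criterion 3, read literally, counts an event-free lost subject as a non-event on an undefined recorded loss date, against the SAP's own last-contact rules

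*SAP*

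**What the plan says.** SAP section 7.9.3.1 defines the estimator at each visit: "the event rate will be calculated as the proportion of the number of subjects with a certain event term over the number of evaluable subjects". An enrolled subject is evaluable by one of three routes:

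- Criterion 1: "Had a clinical or safety event (e.g. MAE) within (on or before) the Reporting cutoff Days, or"
- Criterion 2: "Had a follow-up or days to last contact at or after the lower limit of the Reporting Window"
- Criterion 3: "The Withdrawal Consent Date /Recorded Lost-to-Follow-up Date at or after the lower limit of the Reporting Window"

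The section then names days to MAE and days to last contact as the dates ordinarily used to decide evaluability, and extends the same principle to any adverse event. It also sets out how the last date is found. Deaths take the date of death. Withdrawals, and subjects enrolled but not implanted, take the study exit date. For lost subjects, date rule 3 reads: "For patients who exited study for LTF, complete FU, or other reason, use last known date in the study from", followed by a list of study forms (adverse event, secondary procedure, conversion, clinical and imaging follow-up; otherwise procedure or discharge). Table 3 states each lower limit in terms of last contact; at 12 months it is "Days to last contact: 335 days post-index procedure".

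The SAP does not define the recorded lost-to-follow-up date, and it does not say which rule prevails when that date and the last contact differ.

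**The concern.** Criterion 2 already admits anyone with real contact at or after the lower limit. For a lost subject, criterion 3 can change the result only if the recorded date is later than the last contact. In that case the subject joins the denominator as event-free although nobody saw them near the cutoff. A programmer who follows the numbered list would apply the clause; one who follows date rule 3 and Table 3 would not. The two would report different rates from the same data.

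For event-free lost subjects the clause works in one direction: it lowers the reported proportions for mortality, rupture, secondary procedures, conversion and the other events listed. Long-term safety over 5 years is a stated aim (SAP section 4.2), the data may be used in marketing applications, and with at most 44 subjects each one in the denominator is visible in the result.

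**Working it through.** There is no planned figure to reproduce. SAP section 6 states that "There is no sample size calculation since this study is not a hypothesis driven study" and that "This study will enroll up to 44 subjects". The lower limits and cutoffs in Table 3 agree with the scheduled windows and target days in Table 1 at all seven visits, so the windows are not the problem.

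**1. How the two rules classify one subject (hypothetical dates).** Last contact Day 190, no known event, recorded as lost on Day 760.

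- Criterion 2: 190 < 335 and 190 < 674, so not evaluable at 12 or 24 months.
- Criterion 3, literally: 760 ≥ 335 and 760 ≥ 674, so evaluable and event-free at both.
- Unobserved time before the 24-month cutoff: 730 - 190 = 540 days.

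**2. Unobserved gap allowed before the cutoff (Tables 1 and 3).** Under criterion 2 an event-free subject can be unobserved for at most cutoff minus lower limit:

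- 1 month: 30 - 15 = 15 days
- 6 and 12 months: 183 - 153 = 365 - 335 = 30 days
- 24 to 60 months: for example 1825 - 1769 = 56 days

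Under criterion 3 read literally, take a subject last seen in the previous visit's scheduled window and recorded lost at or after the next lower limit:

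- 60 months (last seen Days 1404-1572): 1825 - 1572 = 253 to 1825 - 1404 = 421 days. The range is the same at 36 and 48 months.
- 24 months (last seen Days 335-421): 730 - 421 = 309 to 730 - 335 = 395 days.

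**3. Effect on the proportion.** Let x be subjects with the event, N the denominator with criterion 3 applied literally, and L the event-free subjects admitted only by a late recorded loss date. The rate is x/N with them and x/(N-L) without them, so the ratio is (N-L)/N whatever x is. With N = 44:

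- L = 1: 43/44 = 0.977, about 2% lower
- L = 8: 36/44 = 0.818, about 18% lower

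The documents give neither x nor L. With assumed values and exact binomial 95% intervals:

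| L | x = 4 | x = 8 |
|---|---|---|
| 0 (all kept) | 4/44 = 9.1% (2.5-21.7) | 8/44 = 18.2% (8.2-32.7) |
| 1 | 4/43 = 9.3% (2.6-22.1) | 8/43 = 18.6% (8.4-33.4) |
| 2 | 4/42 = 9.5% (2.7-22.6) | 8/42 = 19.0% (8.6-34.1) |
| 4 | 4/40 = 10.0% (2.8-23.7) | 8/40 = 20.0% (9.1-35.6) |
| 8 | 4/36 = 11.1% (3.1-26.1) | 8/36 = 22.2% (10.1-39.2) |

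With 4 events the difference is 0.2 to 2.0 percentage points. With L = 0 there is none.

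**4. The last-contact denominator is not unbiased either.** Assume a true risk of 15% by the cutoff, 15% of subjects lost for reasons unrelated to risk, and loss on average halfway, so that about half of a lost subject's risk (7.5%) is observed.

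- Observed events: 0.85 × 0.15 + 0.15 × 0.075 = 0.1275 + 0.01125 = 0.13875.
- All lost subjects kept: 0.13875/1 = 13.9%.
- Event-free lost subjects dropped, lost subjects with events kept by criterion 1: denominator 0.85 + 0.01125 = 0.86125, giving 16.1%.

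One proportion is about 1.1 points below the assumed 15% and the other about 1.1 points above it. Censoring at last contact avoids both errors as long as loss is unrelated to risk.

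**The case against.** The strongest reply is that this is unclear wording, not a settled rule. The recorded date is undefined, and the rest of the section points to last contact. If the recorded date simply means the last known date under date rule 3, the lost-to-follow-up half of criterion 3 adds nothing to criterion 2 and the effect is zero. The protocol pages available show only page headers, so a definition there cannot be excluded. The connector before criterion 3 is also lost at a page break. Reading it as an alternative is an inference, though requiring every followed subject to have a withdrawal or loss date would make no sense. All of this stands, and it is why the point is an unresolved conflict.

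A reader might infer three stronger things that the documents do not support:

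- That the SAP fixes the date as the day a site declares the subject lost. It never says so.
- That every death, stroke or rupture in the gap is scored as a non-event. Any event that becomes known and falls on or before the cutoff counts under criterion 1. Only events that never become known are missed.
- That the rates include unobserved person-time, or that follow-up duration is inflated. The rate is a proportion with no person-time, and duration of follow-up has its own definition in section 7.2.2.

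It is also fair to say that simply deleting the clause introduces an upward selection, as step 4 of the working shows, and that the accountability table in section 7.1.1.2 already shows losses by interval.

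**Conclusion.** The point holds as an internal conflict with a one-sided literal reading. Unless the recorded date equals last contact, criterion 3 lowers MAE and major clinical event proportions to (N-L)/N of their value on the last-contact denominator that date rule 3 and Table 3 imply.

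The size cannot be known from the documents, because the number of losses and any delay in recording them are not given. The range of about 2% to 18% relative rests on the assumption of 1 to 8 such subjects among 44. Late visits may have a smaller N, where the same L weighs more. The comparison is with the last-contact denominator and not with the true risk, which that denominator tends to overstate. Even at 8 subjects the exact intervals overlap widely.

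Severity is modest. The study is descriptive with no hypothesis test, the affected outcomes are additional observations, and the primary observations are assessed at 1 month under sections 7.9.1 and 7.9.2. The change is still worth making because it is cheap and removes either a bias or a redundancy.

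**What to change.** In section 7.9.3.1:

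1. Strike the recorded lost-to-follow-up date from criterion 3 and keep the withdrawal-of-consent date, which matches the exit-date rule for withdrawals.
2. State that subjects lost to follow-up are judged under criterion 2, using the last known date from date rule 3, and that events on or before the cutoff still count under criterion 1.
3. At each annual time point, report beside the proportion a Kaplan-Meier estimate censored at last contact, and say that it assumes loss is unrelated to risk.

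The cost is one line of SAP text, a small programming change that uses a date the SAP already derives, and one extra descriptive analysis. Denominators will be smaller and late rates slightly higher. The Kaplan-Meier estimate is needed because dropping event-free lost subjects, while keeping lost subjects with events, pushes the proportion upward.

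### The itemised sources for the last-contact date in SAP 7.9.3.1 omit the visit or phone-contact date, so event-free subjects last reached by phone may be left out of the event-rate denominators

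*SAP*

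**What the plan says.** SAP 7.9.3.1 covers major adverse events, secondary procedures, rupture, conversion, surgical revascularization of the LSA and paraparesis. It states: "The following observations will be assessed through clinical follow-up (office visit or phone contact"). The rule applied at every visit is that "the event rate will be calculated as the proportion of the number of subjects with a certain event term over the number of evaluable subjects".

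A subject is evaluable by any of three routes:

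1. An event has been recorded no later than the cutoff day.
2. The wording of the second route is "Had a follow-up or days to last contact at or after the lower limit of the Reporting Window".
3. Consent was withdrawn, or loss to follow-up was recorded, no earlier than that limit.

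The section then says that days to MAE and days to last contact are what is usually used to settle evaluability, and that the last contact date draws on every date available from follow-up. A numbered derivation follows:

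- Deaths take the death date, and withdrawals take the exit date.
- Subjects who completed follow-up, were lost, or left for another reason take the last known date from a list of form fields. Item 7 applies the same list to subjects still in the study.
- The listed fields are adverse event start and resolution, secondary procedure, open repair, "i) Date physical exam performed", labs, and "Imaging follow-up Form: Date of diagnostic imaging (including unscheduled imaging"). Procedure or discharge dates are used if there was no follow-up.

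Table 3 expresses every lower limit as days to last contact, for example Day 335 at 12 months and Day 1769 at 60 months.

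**The concern.** The section accepts a phone call as a way of ascertaining these events, but its list gives no field through which a call can advance the last-contact date. A call normally produces neither a physical exam date nor a lab date. The general wording and the itemised list can therefore give different denominators from the same data.

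If the list is followed, exclusion depends on outcome. Someone reached by phone and found event-free can be treated as not evaluable, while someone with an event by the cutoff is kept through criterion 1. Removing only event-free subjects raises the reported rate and shifts its exact interval. With at most 44 subjects (SAP section 6), a few such exclusions would show in the tables.

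**Working it through.** The plan gives no event rate or sample size calculation, so there is no figure to reproduce. The check traces the rules on test records and then illustrates the size.

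**Inputs from the SAP.** Table 3 gives a lower limit of Day 1769 and a cutoff of Day 1825 at 60 months, and a lower limit of Day 335 at 12 months. Evaluability criteria 1 to 3 and the last-known-date list are in 7.9.3.1. Intervals are two-sided 95% exact binomial.

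**Trace of the rules.**

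| Test record | List only | If a call counts as a follow-up or an available date |
|---|---|---|
| A. Event-free; latest listed date Day 1460; phone contact Day 1825; 60 months | Last contact 1460 < 1769: not evaluable | Evaluable |
| B. As A, but the call reports a stroke on Day 1700 | Evaluable by criterion 1 (1700 ≤ 1825) | Evaluable |
| C. Event-free; phone contact Day 365; exam Day 730; 12 months | Last contact 730 ≥ 335: evaluable | Evaluable |
| D. Withdrawal on Day 1800; 60 months | Exit date 1800 ≥ 1769: evaluable | Evaluable |

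A and B differ only in outcome, and that is the source of the bias. C shows that any later listed date restores the earlier time points, so exposure is concentrated at a subject's last time point: 60 months, or the latest visit at the snapshot for an annual report. A and D together show that, on the list, a subject who withdrew can be evaluable when one who completed follow-up by phone is not. SAP 7.2.2 measures follow-up duration to the last follow-up visit or the final assessment on the Study Exit CRF, whichever is later. Subject A could therefore show about 1825 days of follow-up and still be non-evaluable at 60 months.

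**Size, with assumed counts.** Let x be subjects with the event, n the subjects truly followed, and p the event-free subjects with phone-only contact and no later listed date. The intended rate is x/n. The list-only rate is x/(n − p), too high by the factor n/(n − p).

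Assume x = 8 and n = 36:

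- p = 0: 8/36 = 22.2% (95% CI 10.1 to 39.2)
- p = 2: 8/34 = 23.5% (10.7 to 41.2); factor 36/34 = 1.06
- p = 4: 8/32 = 25.0% (11.5 to 43.4); factor 36/32 = 1.13

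Assume x = 4 and n = 44, the enrolment maximum:

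- p = 0: 4/44 = 9.1% (2.5 to 21.7)
- p = 2: 4/42 = 9.5% (2.7 to 22.6)
- p = 4: 4/40 = 10.0% (2.8 to 23.7)

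Intervals are Clopper-Pearson. The values of x and p, and the 36, are illustrative; none comes from the documents.

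**The case against.** The strongest reply is that the SAP never says such subjects are dropped. It calls a phone contact a form of clinical follow-up. Criterion 2 is met by having had a follow-up or by the last-contact date, and the last-contact date is said to use every available date. On that reading subject A is evaluable. This stands to the extent that a reader who infers that phone dates are always ignored goes beyond the text. It does not remove the problem, because the only field-by-field definition of last contact omits the call, and both Table 3 and the sentence on usual practice direct the programmer to that quantity.

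Three further replies hold in part:

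- The list is wider than exam, lab and imaging dates, and later dates repair earlier time points. Table 1 has an imaging window at every scheduled visit, so few subjects may be affected.
- The supplied protocol text is page headers only and no case report form is shown. A call might be dated in the exam field or elsewhere on the form, which cannot be checked.
- Primary safety is a 30-day composite, and the rates at issue are additional observations.

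A reader might also infer that a subject with only a scan in the window is wrongly counted as event-free for stroke or myocardial infarction. An imaging date alone does satisfy the last-contact route, and if nobody asked about events this would pull the rate down. The documents do not make it an error. A scan is a dated contact, it bears on some of the listed events, and statisticians would differ on whether it suffices. Barring such dates from criterion 2 while criterion 1 stayed in place would also remove event-free scan-only subjects and keep those with events, which is the same outcome-dependent denominator.

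**Conclusion.** The point holds as an unresolved conflict within SAP 7.9.3.1. The general wording can include a phone contact, and the itemised sources do not. If the list is what is programmed, event-free subjects whose only contact at or after the lower limit was by phone, and who have no later listed date, leave the denominator, and the event rate is biased upward.

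The number affected is unknown. Under the assumed 8 events in 36, two such subjects add 1.3 percentage points (23.5 − 22.2) and four add 2.8 (25.0 − 22.2). Both shifts are small beside an exact interval of 10.1% to 39.2%. The conclusion assumes that some follow-up is by phone alone and that a call leaves no exam or lab date.

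Severity is minor: the study is a descriptive feasibility study without hypothesis tests, and the primary observations do not depend on late follow-up. The documents do not support saying that the SAP definitely drops these subjects, or that scan and lab dates must be disqualified.

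**What to change.** In the last-known-date list of SAP 7.9.3.1, add to item 4 (clinical follow-up form) the date of follow-up contact, whether by office visit or phone. In criterion 2, state that a follow-up includes a phone contact.

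Keep imaging and lab dates as last-contact sources in the main analysis. If scan-only follow-up is a worry, add at most one sensitivity table of clinical-event rates restricted to subjects with a clinical contact (office or phone) at or after the lower limit. Apply that requirement equally to subjects with and without events, and state how deaths before the lower limit are handled, since those subjects cannot have such a contact.

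The cost is two wording changes and one change to the last-contact derivation, assuming the contact date is already on the form. The sensitivity table is optional extra output.

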7.9.3.2. Aneurysm Diameter Changes

Aneurysm Diameter change will be calculated based on the maximum measurable aneurysm diameter during the post-operative follow-up and each annual follow-up. Reference diameter is the diameter measured at first post-operative follow-up through 1 month. Change of aneurysm diameter will be defined as 1) "increased" if an aneurysm growth is strictly greater than 5 mm of the maximum measurable aneurysm diameter; 2) "decreased" when an aneurysm becomes strictly smaller in size by more than 5 mm; 3) "no change" when the change is within 5 mm.

[figure not shown]
Aneurysm diameter change rates will be calculated separately for increase, decrease and no change based on the number of subjects who had the event divided by number of implanted subjects who are evaluated for aneurysm diameter change at the time point. The analysis time window will be used to determine if an image assessment belongs to a respective time point. The analysis time window for each time point is given in Section 7.2.3.

